### 7.2.3. Primary Safety Outcome Measures

1. Proportion of participants with an adverse event (AE) occurring during any point of the study following randomization.
2. Proportion of participants with a severe adverse event (SAE) occurring during any point of the study following randomization.
3. Proportion of participants with newly acquired transmissible infectious diseases which are considered adverse events of special interest (AESI) after randomization.

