patient's antibiotic treatment plus seven days post-antibiotic treatment.

**Group 2:** This group will receive 30 oral FMT capsules one time 48-72 hours following completion of antibiotic treatment.

**Oral FMT capsules:** Capsules contain fecal microbiota sourced from healthy donors and screened for pathogens.

**Control:** The control is an oral placebo capsule identical to the FMT capsules given to the intervention groups and will be provided by OpenBiome. The placebo capsule consists of glycerol and saline and will be administered daily as five capsules per day during the duration of antibiotic treatment plus an additional seven days post-antibiotic treatment (group 3). Patients will be fasting (clear liquids allowed) for at least 2 hours prior to administration and at a minimum of 1-hr post-administration (Appendix 17.1)

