### **8.2. Inclusion Criteria**

1. Cognitively intact and willing to provide informed consent.
2. Willing and able to comply with all study procedures for the duration of the study.
3. Able to take oral medications.
4. Age 18 or over.
5. Recent CDI episode occurring in the last 90 days with completion of therapy as confirmed by the electronic medical record (EMR)
6. Receiving antibiotics at enrollment for reasons other than CDI and having taken the antibiotics for no longer than 72 hours.
7. Women of childbearing potential in a sexual relationship with men must use an acceptable method of contraception (including, but not limited to, barriers with additional spermicidal foam or jelly, intrauterine devices, hormonal contraception started at least 30 days before enrollment into the study, or intercourse with men who underwent a vasectomy) for 4 weeks following completion of the study treatment.
8. Males must agree to avoid impregnation of women during and for 4 weeks following completion of the study treatment.
9. Able to take the test capsule successfully with no signs or symptoms of dysphagia.\*

\*For patients not receiving treatment during the enrollment visit, the ability to successfully swallow the test capsule can be confirmed the day the intervention is administered.

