##### **8.6.2.1. *Data Collection and Follow-up for Withdrawn Subjects***

If the subject is willing, the coordinator will ask to schedule a close-out study visit to collect a final stool sample and follow-up safety evaluation.

A subject may withdraw from the study at any time for any reason with no consequences. A participant

may be withdrawn from the study by the Investigator for the following reasons:

- Adverse event that may make it no longer in the best interest of the subject to continue to participate
- Recurrent *C.diff* infection
- Participant's choice
- Protocol violation/ non-compliance
- Pregnancy
- Lost to follow-up
- Other (must be noted)

The primary reason for withdrawal from the study will be recorded. Participants will be encouraged to complete the Early Termination Visit. The Early Termination Visit procedures are listed in Section 11.4. Although participants are free to withdraw at any time, subjects will be encouraged to remain in the study for follow-up safety evaluation. Every attempt should be made to follow all AEs and SAEs ongoing at the time of early withdrawal to resolution or until stabilized. If possible, a final stool sample will be collected at the time of Early Termination. All subjects who are randomized will be included in the safety analysis.

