After the baseline clinical assessment and stool sample have been collected, subjects in groups 1 and 3 (daily FMT and daily placebo) are eligible to undergo administration of the intervention (DE or placebo) in

accordance with the randomization schedule. The intervention will be administered by the blinded treatment staff and the participant observed for 30 minutes following administration. Post-ingestion observation of inpatients will only occur after the first dosing; subsequent inpatient dosing will be administered by a study physician/nurse but do not require 30 minutes of observation. Pre-intervention vital signs (as previously described) will be collected or abstracted from the medical record prior to first dose. Participants will be provided with information regarding monitoring for minor and severe adverse event related to the intervention administration. Participants will be encouraged to report any concerning symptoms to staff. Oral nutrition may commence 1 hour post-capsules administration. Study staff do not need to collect a blood sample to check for neutropenia prior to dosing.

For all patients, a baseline stool sample will be collected and all patients should begin to fill out their patient diary starting on Day 0. If a patient is unable to provide a stool sample, peri-rectal swabs may be collected.

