### *Group 2 (single dose FMT): Visit will occur in a clinical setting*

Capsules will be delivered to the patient by a blinded member of the treatment team 48-72 hours following antibiotic treatment completion. If the patient is discharged he/she will be asked to return to the clinic 48-72 hours following completion of his/her antibiotics to consume the 30 capsules under supervision of a nurse or physician. Study staff do not need to collect a blood sample to monitor for neutropenia. During this visit the following will occur:

- Vitals collection
- Physical exam
- Clinical symptoms assessment
- Diet assessment
- Concomitant medications
- Stool sample
- FMT dosing
- Adverse events assessment
- 30 minute post-dose observation

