### 13.1. Specifications of Safety Parameters

#### 13.1.1. ***Definition of Adverse Events (AE)***

Adverse events (AEs) will be recorded at administration of the treatment and during phone calls once the patient is discharged, in the study patient record (source document) as well as on a specific AE case report form (CRF).

An AE is any untoward medical occurrence in a study patient or clinical investigation participant administered a pharmaceutical product. An AE does not necessarily have a causal relationship with this treatment. An AE can therefore be any unfavorable and unintended sign, symptom, or disease temporally associated with the use of a medicinal product, whether or not related to the medicinal product, e.g.:

- any new clinical diagnosis
- any symptom that requires medical clarification or leads to in-patient admission (surgery or accident)
- any suspected adverse drug reaction (ADR)
- any symptom, such as fever, that appears on the study patient's medical records
- any event related in time with the application of the study medication and affecting the health of the study patient (including laboratory value changes)

For the purposes of this study, baseline symptoms will be collected prior to the administration of study intervention. Only those symptoms identified as new or worsened compared to the baseline assessment will be recorded as an AE. In addition, only those abnormal laboratory values or physical examination assessments that are considered clinically significant will be recorded in the study documents.

If there is any doubt as to whether a clinical observation is an AE, the event will be recorded and assessed by the study medical monitor. AEs must be graded for severity and relationship to study product. Adverse events of special interest (AESI) will be defined as newly acquired transmissible infectious diseases.

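### The any-AE outcome counted from randomization to study end dilutes an excess during dosing, and the Group 2 figure includes pre-FMT events; add a treatment-period comparison in matched windows

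*Combined protocol and SAP*

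**What the plan says.** Section 7.2.3 lists three safety outcomes. Item 1 is the "Proportion of participants with an adverse event (AE) occurring during any point of the study following randomization". Item 2 has the same form: "Proportion of participants with a severe adverse event (SAE) occurring during any point of the study following randomization". Item 3 covers newly acquired transmissible infections. Items 1 and 2 count a patient once and set no limit on relatedness or on time since dosing; item 1 sets none on grade either.

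Section 8.6.2.1 fixes the safety set: "All subjects who are randomized will be included in the safety analysis". The AE definition in section 13.1.1 is broad. It includes "any new clinical diagnosis" and symptoms noted in the medical record, related or not, provided they are new or worse than at baseline.

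Patients enter "having taken the antibiotics for no longer than 72 hours" (section 8.2). Groups 1 and 3 can start capsules at baseline (section 11.1). Group 2 receives its capsules "48-72 hours following antibiotic treatment completion" (section 11.2) and no study product before that. AEs are recorded at weekly contacts in every arm during the intervention and the one-month follow-up (section 11.2), then at one call 6 months after FMT completion (section 11.5).

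Sections 7.2.3, 8.6.2.1, 12.2, 12.3 and 13 define no dosed set and no treatment-emergent window for items 1 and 2. Only the solicited symptoms in section 13.2.3 are tied to the time after the intervention.

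**The concern.** Specific aim 2 hypothesizes that oral FMT will be safe in these patients, and section 6 makes safety of both regimens against placebo a secondary objective. Section 5.6 says there are no risk data specific to oral delivery, and section 5.5 says none are published on taking these capsules at home. The safety table is therefore one of the trial's main products.

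A once-per-patient count over about 28 weeks responds weakly to something that acts for about 3. Each later, unrelated event turns a patient who was event-free during dosing into a case, so the arms drift together. In Group 2 the counting period also opens before FMT is given, and patients who never receive it remain in the denominator. CDI before dosing ends participation (section 11.3), and a Group 2 patient may first attempt the test capsule on the dosing day (section 8.2 footnote). A reader of the Group 2 figure could not tell how much of it followed FMT.

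**Working it through.** **The plan's own figure.** No AE rate, safety effect size or power is stated, so there is none to reproduce. The sample size is internally consistent: 3 × 10 = 30, and 8 completers with 20% loss need 8 / 0.80 = 10 per group.

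**Inputs from the protocol**
- Dosing in Groups 1 and 3: a course of up to 14 days (recruitment target, section 8.4.1) plus 7 days = 21 days, or 3 weeks.
- Group 2 before FMT: up to 14 + 3 = 17 days, or 19 + 3 = 22 days at the exclusion limit in section 8.3. A 7-day course (assumed) with 3 days already taken gives 4 + 2 = 6 days.
- Total follow-up: 17 + 180 = 197 days, or 197 / 7 = about 28 weeks.

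**Assumptions.** AE rate constant over time, at 5, 10 or 20% per week (w) or 0.05 to 1.0 per month (r, month = 30.4 days). The effect doubles the rate for the 3 dosing weeks.

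**Formulas**
- Ever/never, weekly: 1 − (1−w)^28 against 1 − (1−2w)^3 (1−w)^25.
- Ever/never, monthly: 1 − exp(−197r/30.4) against 1 − exp(−218r/30.4), since doubling for 21 days adds the equivalent of 21 days.
- First capsule to 28 days after last capsule (3 + 4 = 7 weeks), weekly: 1 − (1−w)^7 against 1 − (1−2w)^3 (1−w)^4. Monthly: 1 − exp(−49r/30.4) against 1 − exp(−70r/30.4).

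| Assumed rate | Ever/never, no effect v doubled (%) | Points | 7-week window, no effect v doubled (%) | Points |
|---|---|---|---|---|
| 5%/week | 76.2 v 79.8 | 3.6 | 30.2 v 40.6 | 10.5 |
| 10%/week | 94.8 v 96.3 | 1.6 | 52.2 v 66.4 | 14.2 |
| 20%/week | 99.8 v 99.9 | 0.1 | 79.0 v 91.2 | 12.1 |
| 0.05/month | 27.7 v 30.1 | 2.5 | 7.7 v 10.9 | 3.1 |
| 0.1/month | 47.7 v 51.2 | 3.5 | 14.9 v 20.6 | 5.7 |
| 0.2/month | 72.6 v 76.2 | 3.5 | 27.6 v 36.9 | 9.3 |
| 0.3/month | 85.7 v 88.4 | 2.7 | 38.3 v 49.9 | 11.5 |
| 0.5/month | 96.1 v 97.2 | 1.1 | 55.3 v 68.4 | 13.0 |
| 1.0/month | 99.8 v 99.9 | 0.1 | 80.0 v 90.0 | 10.0 |

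The ever/never shift is small whether the baseline is 28% or 99.8%, so the dilution does not depend on saturation. One patient in 10 is 10 points. At the lowest rate the window gains little in points (3.1 against 2.5), but the ratio rises from 30.1/27.7 = 1.09 to 10.9/7.7 = 1.4.

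**Pre-FMT events in Group 2.** The chance of an AE in 10 to 14 pre-dose days is 1 − (1−w)^(days/7): 7% (w = 5%, 10 days) to 36% (w = 20%, 14 days). What changes the ever/never figure is the patient who counts only because of such an event. For 14 days this is [1 − (1−w)^2] (1−w)^26 = 2.6%, 1.2% and 0.1% at w = 5, 10 and 20%. Over 6 to 22 days at 0.05 to 1.0 per month it is 0 to 4%. If the rate on antibiotics were 5 times higher (assumed, base 0.1 to 0.3 per month) it would be 4 to 17%.

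**Never-dosed patients.** With 2 of 10 never dosed (assumed, equal to the planned 20% loss), a true 30-point excess in dosed patients becomes 30 × (1 − 2/10) = 24 points.

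**Precision.** At 10 per arm, 10/10 has an exact 95% interval of 69 to 100%. Fisher power for the 7-week contrasts at 5 to 20% per week is only 2 to 3%. Either table can only be descriptive.

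**The case against.** The strongest reply is that counting all randomized patients from randomization is a legitimate comparison of regimens, with the same clock start in every arm. That stands, and it is why the outcome should be kept.

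A reader might go further than the documents allow in four ways.

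- **That the proportion will be near 100% in every arm.** No section gives an any-AE rate for this population, and the assumed rates span 28 to 99.8%. The infusion-trial symptoms in section 5.6.1 are day-of-procedure and colonoscopic, and the 42 AEs in 2,050 patients in Appendix 16.1 come from a stool bank's reporting system. Weekly contact also stops after the one-month follow-up, so a constant recorded rate to 6 months probably overstates both saturation and dilution.
- **That the same holds for SAEs.** Nothing supports saturation for item 2. Only the pre-FMT and never-dosed counting carries over.
- **That Group 2's early events are credited to FMT.** Items 1 and 2 count by randomized arm. Relatedness is judged for each event (section 13.2.2), and a related event must follow FMT administration.
- **That an excess during dosing would go unseen.** There are graded solicited symptoms (section 13.2.3), halting rules on related events (section 13.5.1), DMC review (sections 13.3.2 and 13.6) and item 3.

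It is also fair that a dosed-only set, used as the main comparison, would select Group 2 patients on events after randomization, such as CDI. Dropping Group 2's early events without a matched window in the other arms would add bias.

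**Conclusion.** The point holds as one of sensitivity and interpretation. Item 1 dilutes an on-treatment excess: a doubled rate over 3 weeks moves it by about 4 points or less at every rate assumed. It may saturate, but whether it does depends on an AE rate the documents do not give. The Group 2 proportion mixes events before and after FMT and includes patients never dosed. At a constant rate, pre-FMT events alone shift it by 4 points or less, and by more only if AEs cluster in the antibiotic period. The two problems bite at different rates: where item 1 saturates, early events barely move it.

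The randomized comparison is not biased by any of this. The figures rest on the assumed rates, a constant hazard and an effect confined to 3 dosing weeks, which describes Group 1 and not Group 2's single dose. The 10 to 14 points for the 7-week window apply at 5 to 20% per week; at 0.05 to 0.1 per month the gain in points is small.

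**What to change.** Keep items 1 and 2 in all randomized patients, from randomization, with no early events and no never-dosed patients removed. Add to section 7.2.3 a treatment-period comparison reporting the proportion with at least one AE (all; Grade 2 or higher; related), SAEs, and AEs per patient-week:

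- **Group 1 v Group 3:** onset from first capsule to 28 days after last capsule.
- **Group 2 v Group 3:** onset in the same post-antibiotic period for both, starting at Group 2's 48-72 hour dosing point and running 28 days, in all patients still in follow-up at that point. Give a by-treatment-received version as sensitivity. Neither arm has had active product before that point, so the rule for entering the window treats them alike.
- **Before Group 2's dosing point:** report events separately for all three arms.

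State which baseline defines new or worsened in Group 2 (enrollment or pre-dose). Reconcile the passages that set the windows: the end of follow-up (sections 11.5 and 13.2.3), the antibiotic-course limit (sections 8.3 and 8.4.2.2), the group labels in 8.4.2.2 against those in 9.6, and severe in 7.2.3 item 2 against serious in 13.1.2.

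The cost is wording plus one descriptive table. Onset date, severity, seriousness and causality are already on the AE form (section 13.3.1). The intervals will be wide at 10 per arm, and the text should say so.

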## 8. STUDY SUBJECTS – ENROLLMENT AND WITHDRAWAL

### 8.1. Subject Population

We plan to enroll 30 subjects, 10 subjects per group, with the goal of having eight analyzable subjects who complete trial in each group. Children under 18 years of age will not be included in this study due to the uncertainty of the safety of the proposed intervention in those under 18 in this population. Participants must

meet inclusion criteria and have no exclusion criteria prior to randomization (described below). We expect the study population to be predominantly Caucasian due to the demographics of Dane County. We expect roughly 14% of the subjects to be minorities and half the subjects to be female. There are no study restrictions based on gender or race/ethnicity. Subjects will be patients at the University of Wisconsin Hospitals and Clinics (UWHC). Two groups of subjects from UWHC will be included in this study, inpatients and/or outpatients. Both study populations will have had a CDI within the last 90 days and are on an antibiotic for an unrelated reason and meeting all additional inclusion criteria listed in section 8.2. Both inpatients and outpatients will be identified through medical record review. Inpatients will always be contacted in a clinical setting while outpatients may be contacted by either mail/phone or in the clinic. Outpatients are included in this study as many infections treated with antibiotics are not severe enough to require hospitalization.

### **8.2. Inclusion Criteria**

1. Cognitively intact and willing to provide informed consent.
2. Willing and able to comply with all study procedures for the duration of the study.
3. Able to take oral medications.
4. Age 18 or over.
5. Recent CDI episode occurring in the last 90 days with completion of therapy as confirmed by the electronic medical record (EMR)
6. Receiving antibiotics at enrollment for reasons other than CDI and having taken the antibiotics for no longer than 72 hours.
7. Women of childbearing potential in a sexual relationship with men must use an acceptable method of contraception (including, but not limited to, barriers with additional spermicidal foam or jelly, intrauterine devices, hormonal contraception started at least 30 days before enrollment into the study, or intercourse with men who underwent a vasectomy) for 4 weeks following completion of the study treatment.
8. Males must agree to avoid impregnation of women during and for 4 weeks following completion of the study treatment.
9. Able to take the test capsule successfully with no signs or symptoms of dysphagia.\*

\*For patients not receiving treatment during the enrollment visit, the ability to successfully swallow the test capsule can be confirmed the day the intervention is administered.

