### **8.3. Exclusion Criteria**

1. Admitted to an intensive care unit (ICU).
2. Females who are pregnant, lactating, or planning to become pregnant during the study. Female patients of childbearing potential will take a pregnancy test at the intervention visit and will be excluded if pregnant.
3. Inability (e.g. dysphagia) to or unwilling to swallow capsules.
4. Known or suspected toxic megacolon and/or known small bowel ileus.
5. Bowel obstruction or other gut motility issues occurring in the last two weeks that are unresolved as noted by the patient or in the EMR.
6. Major gastrointestinal surgery (e.g. significant bowel resection) within 3 months before enrollment not including appendectomy or cholecystectomy.
7. History of bariatric or colectomy surgery.

8. Concurrent intensive induction chemotherapy, radiation therapy, or biologic treatment for an active malignancy. Patients on maintenance chemotherapy may be enrolled after consultation with the medical monitor.
9. Expected life expectancy <6 months.
10. Patients with severe anaphylactic or anaphylactoid food allergy.
11. Solid organ transplant recipients ≤90 days post-transplant or on active treatment for rejection.
12. Neutropenia ( $\leq 500$  neutrophils/mL) or other severe immunosuppression. Anti-TNF will be permitted. Patients on monoclonal antibodies to B and T cells, glucocorticoids, antimetabolites (azathioprine, 6-mercaptopurine, methotrexate), calcineurin inhibitors (tacrolimus, cyclosporine), and mycophenolate mofetil may only be enrolled after consultation with the medical monitor.\*
13. At risk of CMV/EBV associated disease, negative IgG testing for cytomegalovirus (CMV) or Epstein Barr Virus (EBV).
14. Any other gastrointestinal illness including diarrhea.
15. On oral vancomycin or metronidazole.
16. Having been taking the currently prescribed antibiotic for over 72 hours.
17. On an antibiotic treatment anticipated to exceed 19 days.
18. Having received an FMT by any route in the 90 days prior to enrollment.
19. Any condition that would jeopardize the safety or rights of the patient, would make it unlikely for the patient to complete the study, or would confound the results of the study.

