#### **8.4.2.2. *Retention***

Stool samples will be taken from all subjects at baseline and every 3 days  $\pm$  1 day regardless of treatment group while the patient is hospitalized. If/when a patient is discharged from the hospital, the patient will continue to provide stool samples every three days during FMT and once weekly for 4 weeks following FMT. We will call or email the patient weekly until they have completed FMT and once weekly during follow-up to remind him/her to mail us a stool sample and discuss the patient diary. If the patient is receiving either the daily FMT or placebo, we will also remind him/her to be taking his/her capsules as well as ask him/her to count how many pills he/she currently has left for us. If a patient in the one-time FMT group is discharged prior to the FMT consumption time point (48-72 hours post antibiotic treatment completion), he/she will be asked to return to the ID clinic or CRU to receive his/her FMT capsules. Inpatients in the daily and placebo groups will have each dose of 5 capsules observed by a nurse/physician during admission and will be discharged with a cooler containing their FMT capsules and instructed on use. Outpatients in the daily and placebo groups will be asked to come to the ID clinic or CRU to have their first dose observed by a nurse or physician and be given the remaining FMT doses to take home. After discharge, all patients will receive a study brochure tailored to their study arm describing all post-discharge study procedures.

While we will target patients who are on antibiotic doses with a duration of less than 14 days, if a patient's antibiotic regimen exceeds 14 days will be handled in the following manner:

Group 1: Patients will be given the 30 capsule dose of FMT on day 16 or 17 (day 14 + 48 to 72 hours) of antibiotic treatment unless they meet one of the criteria for halting a patient's participation in the study (13.5.2). Participants who are not withdrawn from the study will continue follow-up the same as other patients.

Groups 2 and 3: At 14 days of antibiotics, we will discontinue the daily FMT treatments and patients will move to the weekly follow-up phase of the study unless they meet one of the criteria in section 13.5.2 in which case they will be withdrawn from the study.

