## **9.6. Randomization and Blinding of Study Drug**

Participants meeting the eligibility criteria and willing to consent to the study procedures will be randomized on a 1:1:1 basis with block sizes of 10 to receive one of the following treatments:

1. Daily FMT treatment with 5 capsules/day
2. One-time FMT treatment of 30 capsules
3. Daily placebo (5 capsules/day)

Randomization will be carried out by the UW PRC so that the research team and treatment team remains blinded to whether the patient is receiving FMT or placebo.

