### *Group 1 (daily FMT) and Group 3 (daily placebo): Will occur in a clinical setting for inpatients.*

Capsules will be delivered to the patients every day by a blinded member of the treatment team during the time they are admitted. If the patient is discharged or an outpatient, he/she will be provided with enough capsules to complete the study and will be asked to consume 5 capsules per day while on antibiotics as well as for 7 days post-antibiotic treatment completion. Outpatients and patients discharged during the follow-up period will be called or emailed (depending on patient preference) weekly to remind them to take their capsules as well as to send in their stool samples every three days (+/- 1 day). The researcher calling the subject will also ask the subject to count the number of pills he or she has remaining (recorded in the patient diary) and ask about any adverse events or changes to medications and diet. Study staff do not need to collect a blood sample to monitor for neutropenia. If the subject has any capsules remaining after completion of study intervention (e.g. missed doses, shortened antibiotic course after study intervention has been dispensed), the subject will be asked to return the remaining capsules to the Infectious Disease Research lab.

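### Inclusion 7 requires women's contraception only after study treatment, so on its literal terms the dosing period is not covered

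*Combined protocol and SAP*

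**What the plan says.** Section 8.2 item 7 applies to women of childbearing potential in a sexual relationship with men. It lists acceptable methods and ends with its only time window: "intercourse with men who underwent a vasectomy) for 4 weeks following completion of the study treatment". One method in the list carries a start date: "hormonal contraception started at least 30 days before enrollment into the study".

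The next item, for men, reads: "Males must agree to avoid impregnation of women during and for 4 weeks following completion of the study treatment".

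Section 8.3 item 2 excludes women who are pregnant, lactating or planning a pregnancy during the study, and adds: "Female patients of childbearing potential will take a pregnancy test at the intervention visit and will be excluded if pregnant". The study calendar in Section 17.2 places that test at baseline for the two daily groups and at the visit 48 to 72 hours after antibiotics for the single-dose group. It schedules no later test. Section 8.6.2.1 lists pregnancy as a reason for withdrawal.

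On dosing, Section 11.2 has discharged patients and outpatients in the daily groups "consume 5 capsules per day while on antibiotics as well as for 7 days post-antibiotic treatment completion".

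**The concern.** Items 7 and 8 stand next to each other and end in the same phrase. The reference to the treatment period is missing from the one that governs the participants who could become pregnant. A contraception criterion in a trial of an investigational product is there to avoid fetal exposure, and the days on which product is taken are the days of exposure. Item 7 as written protects the month after dosing and does not mention dosing itself.

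Section 11.1 has staff verify the inclusion and exclusion criteria at enrollment. A careful reader who compares the two items could conclude that the rules for men and women differ on purpose. After discharge, and for outpatients after the first dose, capsules are taken at home, so what participants were told is required carries weight.

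**Working it through.** The plan gives no figure to reproduce. The check is a comparison of texts, followed by simple arithmetic for scale.

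**1. Stated windows.**

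| Rule | During treatment | 4 weeks after |
|---|---|---|
| Item 7 (women) | not stated | yes |
| Item 8 (men) | yes | yes |

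**2. Whether another provision fills the gap.**

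- Exclusion 2 (Section 8.3) covers existing and planned pregnancy, not unplanned conception.
- The pregnancy test (Sections 8.3 and 17.2) is done once, at the first dose, and cannot show a conception that happens later.
- Withdrawal for pregnancy (Section 8.6.2.1) and the weekly contacts about adverse events (Section 11.2) act only after conception.
- The 30-day lead-in (Section 8.2 item 7) applies to hormonal methods only. The other methods have no stated start.

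None of these requires contraception while capsules are being taken.

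**3. Which arms are exposed.** Group 3 receives a glycerol and saline placebo (Section 7.1). Group 2 takes one dose, at the visit where its pregnancy test is scheduled. Item 7 also leaves Group 2 without a stated requirement between enrollment and that dose, but no product is taken in that interval. Continuing active exposure after a negative test therefore arises in Group 1.

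**4. Length of Group 1 dosing.** Dosing days = antibiotic days + 7, less up to 3 days because item 6 allows enrollment up to 72 hours into the antibiotic course.

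- 14-day course: 14 + 7 = 21 days; enrolled at the 72-hour limit, 21 − 3 = 18 days.
- Capsules at 5 a day: 5 × 21 = 105; 5 × 18 = 90.
- Assumed 7-day course: 7 + 7 = 14 days; at the limit, 14 − 3 = 11 days.

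Longer courses do not extend this if Section 8.4.2.2 is followed: "At 14 days of antibiotics, we will discontinue the daily FMT treatments". That sentence is labelled for Groups 2 and 3, and the 30-capsule dose beside it is labelled for Group 1. Since Group 2 is the single-dose arm, the labels look transposed, and the rule is read here as applying to the daily groups. If a course at the 19-day limit of exclusion 17 were dosed throughout, the period would be 19 + 7 = 26 days.

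**5. Number of women.** Section 8.1 plans 10 subjects per group and expects half to be female: 10 × 0.5 = 5 in Group 1. The share who are of childbearing potential and in a relationship that item 7 covers is not given, so the range is 0 to about 5.

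**The case against.** The strongest reply is that the literal reading is strained. Section 8.1 requires inclusion criteria to be met before randomization, and contraception begun only after treatment could not be confirmed at that point. Requiring hormonal methods to start 30 days before enrollment makes sense only if contraception is already in use at enrollment. On this view the four weeks mark the end of a period that began earlier. As an account of what the sponsor meant, this is persuasive. It does not settle what the text requires, because the lead-in is attached to one method and the neighboring item shows how the full window is written.

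A second reply is that the consent form or the Manual of Procedures may state the right window. Neither was available, so a gap in practice cannot be shown. Correct wording there would still leave the eligibility criterion with an incomplete window.

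A third reply is that the numbers are small and the harm precautionary. This stands. The available text describes no reproductive risk of the capsules, the upper end of 5 women assumes every woman in Group 1 falls under item 7, and most of the pregnancy risk is handled by exclusion 2 and the first-dose test. It limits the weight of the point without removing it.

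**Conclusion.** The point holds. Item 7 as written sets no contraception requirement on women during study treatment, and no other available section supplies one. The likely cause is a drafting omission. What remains uncovered is unplanned conception after a negative first-dose test in Group 1, over the 18 to 21 days of the longest daily dosing and for 0 to about 5 women. This rests on reading the 14-day stopping rule as meant for the daily groups and on the expected one-half female share. It is a minor participant-safety correction that should be made, with no bearing on sample size, analysis or the primary outcome. Confidence is medium, because the consent form and eligibility checklist could not be seen.

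**What to change.** In Section 8.2 item 7, insert *during and* before the four-week period, to match item 8. Wording that also runs from enrollment would be better, because it would cover Group 2's wait for its dose.

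Apply the change to all three arms. Eligibility is settled before randomization, and under Section 9.6 "the research team and treatment team remains blinded to whether the patient is receiving FMT or placebo", so the rule cannot depend on the arm.

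Check that the consent form and eligibility checklist state the same window, and change them only if they do not.

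The cost is two to four words and one document check. No visit or pregnancy test is added.
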